15.6. SAMPLE SIZE CONSIDERATIONS

In the treatment duration increment part of the study, a 3+3 study design will be utilized, therefore approximately 3-6 patients will be enrolled to define the RP2D.

In the expansion part of the study, a total sample size of 20 patients is proposed; 10 patients with local advanced BCC and 10 patients with metastatic BCC. Assume that CX-4945 is of no interest if its true response is 5% or lower, the proposed sample size for each sub-population will provide an 80% confidence interval of (5.5%, 45.0%) given that there are 2 responses out of the 10 patients. This would provide adequate evidence to suggest that additional studies with this agent may be warranted.

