6. SAMPLE SIZE DETERMINATION

In the treatment-duration-increment part of the study, a 3+3 study design will be utilized, therefore approximately 3-6 patients will be enrolled to define the RP2D.

In the expansion part of the study, a total sample size of 20 patients is proposed; 10 patients with local advanced BCC and 10 patients with metastatic BCC. Assume that CX-4945 is of no interest if its true response is 5% or lower, the proposed sample size for each sub-population will provide an 80% confidence interval of (5.5%, 45.0%) given that there are 2 responses out of the 10 patients. This would provide adequate evidence to suggest that additional studies with this agent may be warranted.

10 patients with metastatic BCC were planned in the expansion part of the study, but only 2 were enrolled due to early termination.

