9. INTERIM ANALYSIS

No interim analysis is planned for this study.

10.DATA CONVENTIONS FOR ANALYSIS

10.1General Statistical Principles

All statistical processing will be performed using SAS® unless otherwise stated. Any statistical tests will be two-tailed at significance level of 0.05 unless otherwise specified.

All observed and derived variables (e.g., change from baseline, percentage change from baseline, and response status) used in the summaries of analyses will be presented in by-subject listings. Unless otherwise noted, the data will be sorted first by treatment assignment, then by subject number and then by date within subject number.

Efficacy and safety results will be summarized descriptively. Categorical parameters will be summarized by the number and percentage of subjects in each category. Denominators for percentages will be appropriate to the purpose of the analysis. Percentages will typically be presented to one decimal (Note: 0% and 100% will be in integer format). Continuous parameters will be summarized as number of subjects, mean, standard deviation (SD), median, minimum, and maximum.

10.2Study Day

Day 1 is defined as the date of first study drug administration. Study day is calculated relative to the date of Day 1. For subjects who did not have a recorded date of first study drug administration, study day will not be calculated.

10.3Baseline and Change from Baseline

Baseline is defined as the last non-missing assessment prior to the first administration of study drug. Change from baseline is defined as post-baseline value minus baseline value unless otherwise specified. Percent change from baseline is (Change from baseline / Baseline) * 100%.

10.4Analysis Visit Window

Results will be summarized according to the visit as recorded in the eCRF. No visit windows will be applied.

10.5Multiple Comparisons

Not applicable. There will be no formal hypothesis testing.

11.STATISTICAL EVALUATION

11.1Subject Disposition

The number and percentage of subjects screened, enrolled, included in key analysis populations, completing the study, and withdrawing from the study (together with the reasons for withdrawal) will be summarized using frequencies and percentages, overall and by cohort (treatment-duration-increment, expansion).

A by-subject listing will show all subjects enrolled and their disposition.

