11.10 Efficacy Analyses

11.10.1Primary Efficacy Analyses

The primary endpoints will be assessed in the Efficacy population, overall and separately for patients with mBCC and patients with locally advanced BCC.

The objective response rate (ORR) will be calculated as the number of patients satisfying the OR criteria divided by the number of subjects in the Efficacy population. Patients without at least one post-baseline response assessment will be treated as non-responders. Further, patients who experience progressive disease but continue treatment under the protocol and experience partial or complete response in a subsequent tumor assessment, will be considered partial or complete responders. A continuity-corrected 95% confidence interval based on the normal approximation will accompany each ORR.

Complete response rates (CRR) will be summarized in parallel fashion to ORR.

11.10.20ther Efficacy Analyses

PFS will be analyzed using the Kaplan-Meier method in the Efficacy population, separately for patients with mBCC and patients with locally advanced BCC.

Summary statistics from the Kaplan-Meier distribution will be determined, including the median and estimates at 3, 6, 9, 12 months. These statistics will be provided as point estimates with 95% confidence intervals.

DOR summary will include at least median (in months), range and patients (n, %) with observed DOR for at least 6 months.

DSD summary will include at least median, range, min, max and patients (n, %) with observed SD for at least 6 months.

DCR summary will include at least median, range, min, max and patients (n, %) with observed DCR for at least 6 months.

Summary of patients with CR+PR+SD (regardless of duration) will include at least median, range, min, max and patients (n, %) with observed CR+PR+SD.

11.10.3Subgroup Analyses

Not applicable.

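### The cohorts are sized on an exact 80% interval for 2/10 that clears 5%, but the SAP reports ORR only with a 95% continuity-corrected normal interval, which at 2/10 includes 5%

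*Protocol*

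**What the plan says.** Protocol 15.6 sets a no-interest rate: "Assume that CX-4945 is of no interest if its true response is 5% or lower". It proposes "10 patients with local advanced BCC and 10 patients with metastatic BCC" for the expansion part and supports that number with an "80% confidence interval of (5.5%, 45.0%) given that there are 2 responses out of the 10 patients". SAP 6 repeats the argument and draws the same conclusion: "This would provide adequate evidence to suggest that additional studies with this agent may be warranted". SAP 6 also records that only 2 of the 10 planned mBCC expansion patients were enrolled, because of early termination.

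Protocol 15.2 names no interval for objective response. SAP 11.10.1 does: "A continuity-corrected 95% confidence interval based on the normal approximation will accompany each ORR". The denominator there is the Efficacy population, which SAP 7 defines to include patients from both the treatment-duration-increment part and the expansion part. Neither document plans an 80% interval or an exact interval for ORR as an output.

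On inference, SAP 10.5 says: "There will be no formal hypothesis testing". SAP 12 says that the SAP follows the protocol's plan without significant change.

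**The concern.** The sizing argument works for one reason: the lower limit of 5.5% lies just above 5%. That depends on both the 80% level and the exact method. The SAP changes both and does not say so. The result that the design section offers as adequate evidence would therefore appear in the ORR table with an interval that comfortably contains the no-interest rate.

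With no test planned, the interval is the only inferential statement attached to ORR. A reader of the study report who compares it with 5% would reach a different view of 2/10 from the one in Protocol 15.6. Nothing in either document says which interval is to be held against 5%.

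**Working it through.** **Inputs.** No-interest rate 5%, n = 10 per cohort, example x = 2, level 80%, limits 5.5% and 45.0% (Protocol 15.6, SAP 6). Reported interval: 95%, normal approximation, continuity-corrected (SAP 11.10.1). Assumption: the documents name no target ORR, so I use 20%, the observed rate in their own example, as the rate of interest.

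**1. Reproduce the design figure.** Clopper-Pearson limits with α = 0.20:

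- lower = Beta quantile(0.10; x, n − x + 1) = Beta(0.10; 2, 9) = 5.45%
- upper = Beta quantile(0.90; x + 1, n − x) = Beta(0.90; 3, 8) = 44.96%

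These round to the stated 5.5% and 45.0%, so the design figure is correct and the method is the exact one. Other 80% formulas do not match it: uncorrected normal gives 3.8% to 36.2% and Wilson 8.6% to 39.8%.

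**2. The interval the SAP plans, at 2/10.** p ± [z·√(p(1 − p)/n) + 1/(2n)], with p = 0.20 and z = 1.96:

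- √(0.20 × 0.80/10) = 0.1265
- half-width = 1.96 × 0.1265 + 0.05 = 0.298
- limits: −9.8% to 49.8% (0% to 49.8% if truncated at zero)

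This includes 5%.

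**3. Separate level from method, at 2/10.**

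| | 80% | 95% |
|---|---|---|
| Exact | 5.5% to 45.0% (excludes 5%) | 2.5% to 55.6% (includes 5%) |
| SAP formula | −1.2% to 41.2% (includes 5%) | −9.8% to 49.8% (includes 5%) |

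Only the combination used in Protocol 15.6 excludes 5%. Changing the level alone, or the method alone to exact, does not bring the SAP output back into line with it.

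**4. Fewest responses in 10 with a lower limit above 5%.**

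- Exact 80%: 1/10 gives 1.0%, 2/10 gives 5.45%, so 2.
- SAP interval: 3/10 gives −3.4%, 4/10 gives 4.6%, 5/10 gives 14.0%, so 5.

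**5. Chance of reaching each count** (binomial, n = 10):

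| True ORR | At least 2 | At least 5 |
|---|---|---|
| 5% | 8.6% | 0.006% |
| 20% | 62.4% | 3.3% |

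For example, P(X ≥ 2 at 5%) = 1 − 0.95^10 − 10 × 0.05 × 0.95^9 = 1 − 0.599 − 0.315 = 0.086.

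**6. Sensitivity to the denominator.** The ORR denominator can exceed 10, because run-in patients are pooled in. With one run-in patient added, 2/11 has an exact 80% lower limit of 4.95%, already below 5%; 2/13 gives 4.17%. For mBCC, counting the 2 expansion patients alone, 1/2 would give an exact 80% lower limit of 5.13%, which nobody would read as the evidence Protocol 15.6 describes.

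**The case against.** The best reply is that Protocol 15.6 is a precision illustration. The primary endpoint is the RP2D, objective response is secondary, efficacy is summarised descriptively and no test is planned. Using one confidence level for sizing and another for reporting is not in itself an error. The 5% rate, the 80% level and the 2/10 example are also fixed in writing, and anyone with the responder count and the denominator can compute the 80% interval. Much of this stands, and it sets the weight of the point. It does not remove the inconsistency: the documents attach a conclusion to 2/10, and the planned table would show that same result as compatible with a drug of no interest, without comment.

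Three stronger readings are tempting and are not supported.

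- A reader might infer that a go/no-go rule has been contradicted. Neither document states such a rule. The wording is that further studies may be warranted.
- A reader might infer that the trouble is the 95% level alone and would persist under any formula or denominator. It would not: an uncorrected Wilson 95% interval at 2/10 is 5.7% to 51.0%, and the exact 95% lower limit at 2/5 is 5.27%; both exclude 5%. Neither is the planned interval at the planned size, but they rule out the general claim.
- A reader might measure the gap with an exact 95% interval, under which 3/10 is needed (32% chance at a true ORR of 20%, 1.2% at 5%). The SAP does not plan that interval. Under the one it does plan, the figures are 5/10, 3.3% and 0.006%.

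**Conclusion.** The point holds as an inconsistency between the design rationale and the planned reporting. The stated 80% interval is correct, but the planned ORR table contains no interval that reproduces it, and the planned one at 2/10 includes 5%. Read against 5%, the planned interval moves the needed count from 2 to 5 in 10.

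This rests on n = 10 per cohort, on the usual form of the continuity-corrected normal interval, and, for the 62% and 3.3% figures, on an assumed true ORR of 20%. The finding that the planned interval includes 5% at 2/10 needs no assumed response rate. SAP 6 states no shortfall for locally advanced BCC, so the point is live there. For mBCC, with 2 expansion patients, the 10-patient argument no longer applies under any interval. The endpoint is secondary and descriptive, so the consequence is an ambiguous reading of activity, not a failed analysis.

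**What to change.** In SAP 11.10.1:

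- Add an exact (Clopper-Pearson) two-sided 80% interval for ORR, computed in the expansion patients of each disease cohort, which is the denominator Protocol 15.6 uses.
- State that this is the interval read against 5%, and label the 95% interval supplementary.
- State that the 2/10 reading does not apply to mBCC, because only 2 expansion patients were enrolled.

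Alternatively, if the sponsor wants 95% as the level of evidence, restate Protocol 15.6 and SAP 6 to say that 2/10 does not exclude 5% with the interval to be reported.

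The cost is one extra column in the ORR table and a few sentences, with no new data. The small downside of the first option is that the 80% level must be labelled openly as a nominal 10% one-sided error (8.6% actual at 2/10 against 5%).

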15.7. DATA QUALITY ASSURANCE

The CRO will perform oversight of the data management of this trial. The CRO will produce an EDC Study Specification document that describes the quality checking to be performed on the data. Central Laboratory data will be sent directly to the CRO, using its standard procedures to handle and process the electronic transfer of these data. eCRFs and data queries documentation will be maintained in the EDC system's audit trail. System backups for data stored at the CRO and records retention for the study data will be consistent with the CRO's standard procedures.

16. ASSESSMENT OF SAFETY

16.1. SAFETY VARIABLES AND DEFINITIONS

Safety assessments will consist of monitoring and recording protocol-defined adverse events (AEs) and serious adverse events (SAEs); measurement of protocol-specified hematology, clinical chemistry, and urinalysis variables; measurement of protocol-specified vital signs; and other protocol-specified tests that are deemed critical to the safety evaluation of the study drug.

Senhwa Biosciences is responsible for reporting relevant SAEs to the Competent Authority, other applicable regulatory authorities, and participating investigators, in accordance with regulatory requirements.

Senhwa Biosciences or its designee is responsible for reporting unexpected fatal or life-threatening events associated with the use of the study drug to the regulatory agencies and competent authorities by telephone or facsimile within 7 calendar days after being notified of the event. Senhwa Biosciences or its designee will report other relevant SAEs associated with the use of the study drug to the appropriate competent authorities (according to local guidelines), investigators, and central IRBs/ECs (except in the United States where investigators are responsible for

reporting to their IRBs per local requirements) by a written safety report within 15 calendar days of notification.

16.1.1. Adverse Event

An AE is any unfavorable and unintended sign, symptom, or disease temporally associated with the use of an investigational medicinal product or other protocolimposed intervention, regardless of attribution.

This includes the following:

- AEs not previously observed in the patient that emerge during the protocol-specified AE reporting period, including signs or symptoms associated with advanced BCC that were not present prior to the AE reporting period (see Section 16.2.1)
- Complications that occur as a result of protocol-mandated interventions (e.g., invasive procedures such as biopsies)
- AEs that occur prior to assignment of study treatment that are related to a protocol-mandated intervention (e.g. invasive procedures such as biopsies, medication washout, or no treatment run-in).
- Preexisting medical conditions (other than the condition being studied), judged by the investigator to have worsened in severity or frequency or changed in character during the protocol-specified AE reporting period.
- 16.1.2. Serious Adverse Event

An SAE is any AE that is any of the following:

- Is fatal (i.e., the AE actually causes or leads to death)
- Is life threatening (i.e., the AE, in the view of the investigator, places the patient at immediate risk of death)
- Requires or prolongs inpatient hospitalization
- Results in persistent or significant disability/incapacity (i.e., the AE results in substantial disruption of the patient's ability to conduct normal life functions)
- Results in a congenital anomaly/birth defect in a neonate/infant born to a mother exposed to the investigational product(s)
- Is considered a significant medical event by the investigator (e.g., may jeopardize the patient or may require medical/surgical intervention to prevent one of the outcomes listed above)

All AEs that do not meet any of the criteria for serious should be regarded as nonserious AEs.

The terms "severe" and "serious" are not synonymous. Severity refers to the intensity of an AE (as in mild, moderate, or severe pain); the event itself may be of relatively minor medical significance (such as severe headache). "Serious" is a regulatory definition and is based on patient or event outcome or action criteria

usually associated with events that pose a threat to a patient's life or vital functions. Seriousness (not severity) serves as the guide for defining regulatory reporting obligations.

Severity and seriousness should be independently assessed when recording AEs and SAEs on the eCRF.

16.1.3. Other Protocol Reportable Events - Pregnancy Reporting

If a patient becomes pregnant during the course of the study, the investigational agent should be discontinued immediately.

Pregnancy itself - occurring in female participants, and female partners of male participants - is not regarded as an AE unless there is a suspicion that the IP under study may have interfered with the effectiveness of a contraceptive medication. The outcome of all pregnancies (spontaneous miscarriage, elective termination, ectopic pregnancy, normal birth, or congenital abnormality) should be followed up and documented even if the patient was discontinued from the study.

The investigator is required to report to the CRO any pregnancy occurring in female participants, and female partners of male participants. Pregnancies occurring up to 6 months after the last dose of study treatment must also be reported.

The investigator should report the pregnancy in a timely manner, within 24 hours of learning. All follow-up reports must be submitted to the CRO in a timely manner. For pregnant partner of trial participant (and pregnant participants, if required by local policy), a copy of the signed signature page of the pregnancy follow-up consent must be submitted to the CRO.

If the pregnancy results in death (e.g. spontaneous abortion, stillbirth); is lifethreatening; requires inpatient hospitalization or prolongation of existing hospitalization; results in persistent or significant disability/incapacity; is a congenital anomaly/birth defect, then an SAE report must be additionally submitted as described above. Please note, hospitalization for labor/delivery alone does not constitute an 'inpatient hospitalization' for the purposes of pregnancy reporting. Refer to Section 16.4.2 for SAE reporting instructions.

16.2. METHODS AND TIMING FOR CAPTURING AND ASSESSING SAFETY PARAMETERS

The investigator is responsible for ensuring that all AEs and SAEs (as defined in Section 16.1) are recorded on the eCRF and reported to the CRO in accordance with protocol instructions.

16.2.1. Adverse Event Reporting Period

After informed consent, but prior to initiation of study drug, only SAEs caused by a protocol-mandated intervention will be collected (e.g., SAEs related to invasive procedures such as biopsies, medication washout, or no treatment run-in).

After initiation of study drug, all AEs and SAEs regardless of attribution will be collected until 30 days following the last administration of study treatment or study discontinuation/termination, whichever is later. After this period, investigators should report only SAEs that are felt to be related to prior study treatment (see Section 16.6). Additional guidance is provided for pregnancy events occurring within 6 months after the last dose of CX-4945 in Section 16.1.3.

16.2.2. Assessment of Severity and Causality of Adverse Events

Investigators will seek information on AEs and SAEs at each patient contact. All AEs and SAEs, whether reported by the patient or noted by authorized study personnel, will be recorded in the patient's medical record and on the appropriate AE/SAE eCRF.

For each AE and SAE recorded on the applicable eCRF, the investigator will make an assessment of seriousness (see Section 16.1.2 for seriousness criteria), severity, and causality.

The following criteria provides guidance for grading AE severity. The AE grading (severity) scale found in the CTCAE, v5.0, will be used for AE reporting.

| 1. | Mild: | Nuisance, barely noticeable. | | | | | |
|----|-------------------|---|--|--|--|--|--|
| 2. | Moderate: | Uncomfortable, troublesome symptoms not significantly interfering with daily activities or sleep. | | | | | |
| 3. | Severe/Disabling: | Symptoms significantly interfere with daily activities or sleep. | | | | | |
| 4. | Life threatening: | Event places the patient at risk of death. | | | | | |
| 5. | Fatal: | Event caused the death of the patient. | | | | | |

To ensure consistency of causality assessments, investigators should apply the following general guidelines:

Is the AE/SAE suspected to be caused by the investigational product based on facts, evidence, science-based rationales, and clinical judgment?

| | The temporal relationship of the AE/SAE to investigational | | |
|-----|--|--|--|
| YES | product administration makes a causal relationship possible, | | |
| | AND other drugs, therapeutic interventions or underlying | | |
| | conditions do not provide sufficient explanation for the AE/SAE. | | |
| | The temporal relationship of the AE/SAE to investigational | | |
| NO | product administration makes a causal relationship unlikely, OR | | |
| | other drugs, therapeutic interventions or underlying conditions | | |
| | provide a sufficient explanation for the AE/SAE. | | |

Note: The investigator's assessment of causality for individual AE reports is part of the study documentation process. Regardless of the "Yes" or "No" causality assessment for individual AE reports, the Sponsor will promptly evaluate all reported SAEs against cumulative product experience to identify and expeditiously communicate possible new safety findings to investigators and applicable regulatory authorities.

16.3. PROCEDURES FOR RECORDING ADVERSE EVENTS

16.3.1. Recording Adverse Events on the eCRF

Investigators should use correct medical terminology/concepts when recording AEs or SAEs on the eCRF and should avoid colloquialisms and abbreviations. Only one medical concept should be recorded in the event field on the AE/SAE eCRF page.

A. Diagnosis versus Signs and Symptoms

If known, a diagnosis should be recorded on the eCRF rather than individual signs and symptoms (e.g., record only liver failure or hepatitis rather than jaundice, asterixis, and elevated transaminases). However, if a constellation of signs and/or symptoms cannot be medically characterized as a single diagnosis or syndrome at the time of reporting, each individual event should be recorded as an AE or SAE on the eCRF. If a diagnosis is subsequently established, it should be reported as follow-up information.

B. Adverse Events Occurring Secondary to Other Events

In general, AEs occurring secondary to other events (e.g., cascade events or clinical sequelae) should be identified by their primary cause. For example, if severe diarrhea is known to have resulted in dehydration, it is sufficient to record only diarrhea as an AE or SAE on the eCRF.

However, medically significant AEs occurring secondary to an initiating event that are separated in time should be recorded as independent events on the eCRF. For example, if a severe gastrointestinal hemorrhage leads to renal failure, both events should be recorded separately on the eCRF.

C. Persistent or Recurrent Adverse Events

A persistent AE is one that extends continuously, without resolution between patient evaluation timepoints. Such events should only be recorded once on the eCRF unless their severity increases. If a persistent AE becomes more severe, it should be recorded again on an AE/SAE eCRF.

A recurrent AE is one that occurs and resolves between patient evaluation timepoints and subsequently recurs. All recurrent AEs should be recorded on an AE/SAE eCRF.

D. Abnormal Laboratory Values

Only clinically significant laboratory abnormalities that require active management will be recorded as AEs or SAEs on the eCRF (e.g., abnormalities that require study drug dose modification, discontinuation of study treatment, more frequent follow-up assessments, further diagnostic investigation, etc.).

If the clinically significant laboratory abnormality is a sign of a disease or syndrome (e.g., alkaline phosphatase and bilirubin $5 \times$ the upper limit of normal associated with cholecystitis), only the diagnosis (e.g., cholecystitis) needs to be recorded on the AE/SAE eCRF.

If the clinically significant laboratory abnormality is not a sign of a disease or syndrome, the abnormality itself should be recorded as an AE or SAE on the eCRF. If the laboratory abnormality can be characterized by a precise clinical term, the clinical term should be recorded as the AE or SAE. For example, an elevated serum potassium level of 7.0 mEq/L should be recorded as "hyperkalemia."

Observations of the same clinically significant laboratory abnormality from visit to visit should not be repeatedly recorded as AEs or SAEs on the eCRF, unless their severity, seriousness, or etiology changes.

E. Deaths

Deaths that occur during the protocol-specified AE reporting period (see Section 16.2.1) that are attributed by the investigator solely to progression of advanced BCC will be recorded only on the Study Discontinuation eCRF. All other on-study deaths, regardless of attribution, will be reported to the Clinical Safety Management at the CRO within 24 hours of learning of the events. Refer to Section 16.4.2 for reporting instructions.

When recording a death on an SAE eCRF, the event or condition that caused or contributed to the fatal outcome should be recorded as the single medical concept on the SAE eCRF. If the cause of death is unknown and cannot be ascertained at the time of reporting, record "Unexplained Death" on the SAE eCRF.

F. Preexisting Medical Conditions

A preexisting medical condition is one that is present at the start of the study. Such conditions should be recorded on the Medical and Surgical History eCRF. A preexisting medical condition should be recorded as an AE or SAE only if the frequency, severity, or character of the condition worsens during the study. When

recording such events on an AE/SAE eCRF, it is important to convey the concept that the preexisting condition has changed by including applicable descriptors (e.g., "more frequent headaches").

G. Worsening of Advanced Basal Cell Carcinoma

Worsening and/or progression of advanced BCC should not be recorded as an AE or SAE. These data will be captured as efficacy assessment data only.

H. Hospitalization, Prolonged Hospitalization or Surgery

Any AE that results in hospitalization or prolonged hospitalization should be documented and reported as an SAE unless specifically instructed otherwise in this protocol.

There are some hospitalization scenarios that do not require reporting as an SAE when there is no occurrence of an AE. These scenarios include a planned hospitalization or prolonged hospitalization to:

- Perform an efficacy measurement for the study
- Undergo a diagnostic or elective surgical procedure for a preexisting medical condition that has not changed
- Receive scheduled therapy for the target disease of the study

I. Pregnancy

Pregnancy is reportable event. The CRO must be notified within 24 hours of learning of the pregnancy to facilitate outcome follow-up. Please refer to Section 16.1.3 for additional specific instructions.

16.4. EXPEDITED REPORTING REQUIREMENTS FOR SERIOUS ADVERSE EVENTS AND OTHER PROTOCOL REPORTABLE EVENTS

